- 6-months confirmed disability progression (6MCDP), is used in the IAP to keep consistent with the parent study IAP, although 3 months confirmed disability progression, 3MCDP, is defined in the CSP.
- As data provided from MRI vendor only contains absolute values for (all) T1-Gd+ lesions per assessment (no new T1-Gd+ lesions), in consequence (all) T1-Gd+ lesions per assessment will be used for definition of disease activity and for calculation of Combined Unique Active (CUA) lesions during MAGNIFY MS Extension Study. However, as MAGNIFY MS Extension Study only has yearly MRI assessments the number of "new" and "all" T1-Gd+ lesions can be considered identical (see also explanation in Section 9.8).

8 Analysis Sets and Subgroups

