Period 12.1 (p_{12.1}) is defined as the Period between Baseline to Month 12 MRI scans,

Period 12.2 (p_{12.2}) is defined as the Period between Month 12 to Month 24 MRI scans,

Period 12.3 (p_{12.3}) is defined as the Period between Month 24 to Month 36 MRI scans,

Period 12.4 (p_{12.4}) is defined as the Period between Month 36 to Month 48 MRI scans.

2-Year Period:

Period 24.1 (p_{24.1}) is defined as the Period between Baseline to Month 24 MRI scans.

3-Year Period:

Period 36.1 (p_{36.1}) is defined as the Period between Baseline to Month 36 MRI scans.

4-Year Period:

Period 48.1 (p_{48.1}) is defined as the Period between Baseline to Month 48 MRI scans.

Sequential Visit Periods:

For p_{100.0}, p_{100.1}, p_{100.2}, p_{100.3}, p_{100.6}, p_{100.12}, p_{100.15}, p_{100.18}, p_{100.24}, see Section 9 of MAGNIFY MS IAP version 3.0.

Period 100.36 ($p_{100.36}$) is defined as the Period between Month 24 to Month 36 (equivalent to $p_{12.3}$) MRI scans.

Period 100.48 ($p_{100.48}$) is defined as the Period between Month 36 to Month 48 (equivalent to $p_{12.4}$) MRI scans.

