9.8 Data Handling for MRI data

MRI data will be integrated with MRI data from the MAGNIFY MS trial, which will be handled according to "Data Handling for MRI data – Data handling of Tertiary endpoints" in Section 9 of the MAGNIFY MS IAP version 3.0.

The MRIs will be evaluated by independent central review. The assignment of MRIs to the respective Visits in the parent study was ensured by the central reading process, while this process is not adopted in the Extension Study. Therefore, the statistical analysis will be based on the MRI Visit assignments as provided by central reading for parent study data and MRI Visit assignments as reported in the eCRF for Extension Study data. A 6-months window will be allowed for the Extension Study MRI data. An MRI assessment will be excluded from all analyses if the absolute value of (MRI assessment date – Visit date) > 185 days (which is obtained by 180 [6 months] + 5 [window allowed by protocol]).

All derived lesion counts (except for the Mean T1 Gd+ lesion count) as specified below will be classified as Not Evaluable (NE) if one of the components required for the calculation has been classified as NE by the central reading. The Mean T1 Gd+ lesion count will be set to NE only, if all T1 Gd+ lesion counts that correspond to the respective Period are classified as NE. In all other cases the mean will be calculated based on the available counts during the respective Period.

For definition of Period see Section 9.6 "Study Periods for MRI Assessments".

T1 Gd+ lesion count

- The T1 Gd+ are defined as follow: T1 Gd+ lesion count (by Visit) = T1 Gd+ lesions count from the MRI at the respective Visit.
- Mean T1 Gd+ lesion count (by Period) = sum of all T1 Gd+ lesion counts during the Period /# of scans belonging to the respective Period with non-missing T1 Gd+ lesion count.

All MRI scans belonging to a Period are MRI scans that have been performed during the Period including start and end Visits. For post-Baseline periods starting at Baseline, the Baseline Visit will not be included. For example, Period 48.1 will include all MRI scans during both MAGNIFY MS trial and Extension Study except Screening and Baseline Visit.

- New T1 Gd+ lesion count (by Period)
 - For Periods including up to Month 24 Visit, refer to "Data handling for MRI data: Data handling of Tertiary endpoints" in Section 9 of MAGNIFY MS IAP version 3.0
 - For other Periods ending at Month 36 / Month 48 Visit,

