 New T1 Gd+ lesion count = T1 Gd+ lesions count from the MRI at Month 36 / Month 48 Visit due to longer periods

For example: New T1 Gd+ lesion count of the Period between Month 24 and Month 36 (p12.3) is equal to T1 Gd+ lesion count from the MRI at Month 36 Visit.

Active T2 lesion count

As the active (i.e., the new or enlarging) T2 lesion count depends on the length of the Period, it will be presented as reported (non-standardized) and annualized (standardized to 1 years (365.25 days)):

- Period length (days) = MRI date at end of Period MRI date at start of Period +1,
- Annualized active T2 lesion count (by Period) = Total number of active T2 lesions per Period * 365.25/ Period length.

The following types of T2 lesions are defined per Period (standardized and non-standardized):

- Total new T2 lesion count =
 - Total number of new T2 lesions with T1 Gd+
 - + Total number of new T2 lesions without T1 Gd+
- Total enlarging T2 lesion count =

Total number of enlarging T2 lesions with T1 Gd+

- + Total number of enlarging T2 lesions without T1 Gd+
- Total active T2 lesion count =

Total new T2 lesion count

+ Total enlarging T2 lesion count

Note: the number of new or enlarging T2 (with and without T1 Gd+) will be provided by central reading for each of the Periods including the Sequential Visit Periods.

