9.10 Covariates and Stratification Factors

The following covariates are defined:

Unless otherwise specified, these factors will be obtained from the baseline information of the MAGNIFY MS Baseline.

Age

See MAGNIFY MS IAP version 3.0.

EDSS at Baseline

see MAGNIFY MS IAP version 3.0.

Pooled centers

Some centers will have few eligible participants only. Therefore, the centers will be pooled together by country except for

• sites that have more than 12 participants in the FAS (i.e., these sites will not be pooled with any other site).

Some countries will have few eligible participants only. Therefore, countries will be pooled as follows:

- Scandinavia = Finland and Sweden
- Mediterranean = Italy and Spain
- o France-UK = France and UK
- o Austria-Hungary-Czech = Austria, Hungary, and Czech Republic
- Australia-Canada = Australia and Canada

The following MRI specific covariate is defined:

Time between scans: in Years

Time between scans (in Years) is calculated as follows:

- Time between scans (in Years) = (MRI date of the Visit MRI of the previous Visit + 1) /365.25, i.e.:
 - If (Visit= Month 36) then Time between scans (in Years) = (MRI date at Month 36
 MRI date at Month 24 + 1)/365.25
 - If (Visit= Month 48) then Time between scans (in Years) = (MRI date at Month 48
 MRI date at Month 36 + 1)/ 365.25

If the corresponding MRI is available and the time between scans is missing (due to preceding MRI being missing) it will be replaced by expected time as follows:

- Month 36 Visit = 1 year
- Month 48 Visit = 1 year

For calculations for Month 1, 2, 3, 6, 12, 15, 18, 24 Visits, see MAGNIFY MS IAP version 3.0 Section 9.

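### SAP 9.8 sets the new T1 Gd+ lesion count for Baseline–M36 and Baseline–M48 to the last scan's count alone, so the three- and four-year values ignore earlier scans and can fall as the Period lengthens

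*SAP*

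**What the plan says.** SAP Section 9.6 defines the MRI Periods. Besides the one-year Periods, it has a three-year Period, p36.1, which "is defined as the Period between Baseline to Month 36 MRI scans", and a four-year Period, p48.1, which "is defined as the Period between Baseline to Month 48 MRI scans".

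SAP Section 9.8 then gives two rules for the new T1 Gd+ count by Period. Periods up to Month 24 follow the parent-study analysis plan (MAGNIFY MS IAP version 3.0). The second rule is introduced by "For other Periods ending at Month 36 / Month 48 Visit" and reads "New T1 Gd+ lesion count = T1 Gd+ lesions count from the MRI at Month 36 / Month 48 Visit due to longer periods". No exception is made for p36.1 or p48.1. The only worked example is a one-year Period, valued on its Month 36 scan: "New T1 Gd+ lesion count of the Period between Month 24 and Month 36 (p12.3) is equal to T1 Gd+ lesion count from the MRI".

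The reason is given in SAP Section 7. The imaging vendor supplies only the total Gd+ count per scan in the extension, and because "MAGNIFY MS Extension Study only has yearly MRI assessments the number of 'new' and 'all' T1-Gd+ lesions can be considered identical", the total is used in place of the new count.

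For the mean T1 Gd+ count, Section 9.8 takes all scans in the Period and gives this illustration: "Period 48.1 will include all MRI scans during both MAGNIFY MS trial and Extension Study except Screening and Baseline Visit".

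**The concern.** The yearly-scan argument justifies treating every lesion seen at M36 as new since Month 24, and every lesion seen at M48 as new since M36. It says nothing about the scans between Baseline and Month 24, which also lie inside p36.1 and p48.1, or about the M36 scan, which lies inside p48.1. Read as written, the rule gives those two Periods a last-scan value under a label that suggests new lesions over three or four years.

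At stake is the meaning of any table of new T1 Gd+ lesions over the combined parent and extension period. A reader would take it as a total over the Period. The number shown could be zero for a participant who had lesions on several earlier scans, next to a positive mean Gd+ count for the same Period.

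**Working it through.** **Inputs.**
- Rule and scope: SAP 9.8, as quoted. The Periods ending at M36 or M48 in SAP 9.6 are p12.3, p100.36, p36.1, p12.4, p100.48 and p48.1.
- Parent-study scans: SAP 9.10 lists eight post-Baseline visits in its MRI covariate rule ("For calculations for Month 1, 2, 3, 6, 12, 15, 18, 24 Visits, see MAGNIFY MS IAP version 3.0 Section 9"). Adding M36 gives up to 8 + 1 = 9 scans in p36.1. Adding M48 gives up to 10 in p48.1.
- Lesion rate per scan: not in the documents, so assumed below.

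**Step 1. Apply the rule.** Let c(m) be the T1 Gd+ count at month m.
- p12.3 = p100.36 = p36.1 = c(36)
- p12.4 = p100.48 = p48.1 = c(48)

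So p36.1 uses 1 of up to 9 scans and p48.1 uses 1 of up to 10. The three-year value is identical to the Year 3 value, and the four-year value to the Year 4 value.

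**Step 2. Ordering.** p48.1 contains p36.1, which contains p12.3. With c(36) = 1 and c(48) = 0, the rule gives p12.3 = 1, p36.1 = 1 and p48.1 = 0. The longer Period has fewer new lesions than a Period inside it.

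**Step 3. One constructed participant.** Take c(1) = 2, c(2) = 1, c(36) = 1 and zero elsewhere, with all scans available and each lesion new when first seen.

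| Quantity | p36.1 | p48.1 |
|---|---|---|
| New T1 Gd+ count, SAP rule | 1 | 0 |
| Sum over scans | 2 + 1 + 1 = 4 | 4 |
| Mean T1 Gd+ count, SAP rule | 4/9 = 0.44 | 4/10 = 0.40 |

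For p48.1 the two SAP measures disagree: a mean of 0.40 per scan and a new-lesion count of 0.

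**Step 4. How often the count would fall.** Assume c(36) and c(48) are independent Poisson counts with the same mean λ. Then P(p48.1 < p36.1) = P(c(48) < c(36)) = [1 − P(c(36) = c(48))]/2.

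| Assumed λ per scan | P(p48.1 < p36.1) |
|---|---|
| 0.05 | 4.6% |
| 0.1 | 8.7% |
| 0.2 | 15.1% |
| 0.5 | 26.7% |
| 1.0 | 34.6% |

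**Step 5. Which endpoints use the Period count.** SAP 14.1.1 and 14.2.1 date a NEDA-3 MRI event at the first scan showing a T1 Gd+ or active T2 lesion. SAP 14.2.2 uses the same event dates. SAP 14.2.3 dates the first new T1 Gd+ lesion at the first scan on which one is found. A lesion at Month 3 or M36 is therefore an event whatever value p48.1 takes.

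**The case against.** The best defence is that the SAP says by Period, not cumulative, and defines each Period by its bounding scans. The closing words of the rule, about longer periods, could mean a comparison of the end scan with the start scan: over a long interval, every lesion enhancing at the end is new relative to the start. On that reading a fall from p36.1 to p48.1 is no contradiction. This stands in part, because it makes the rule coherent. But the SAP does not state that reading, and the result would still be a point count on the last scan under a three- or four-year new-lesion label.

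Three stronger inferences are tempting, and the documents do not support them.
- *That the primary result or a time-to-event endpoint is biased.* Step 5 shows that they are decided scan by scan.
- *That CUA lesions over the combined period are understated.* SAP Section 7 ties CUA to per-assessment Gd+ counts during the Extension Study. The exploratory sections are redacted, so no visible output feeds p36.1 or p48.1 into CUA.
- *That the rule biases a treatment comparison in the drug's favour.* The study is single-arm and tests no formal hypothesis (Protocol 9.1). The most that can be said is that a last-scan count can equal a sum over scans or fall below it, never exceed it.

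**Conclusion.** The point holds as a derivation and labelling defect in SAP 9.8, confined to the new T1 Gd+ count for p36.1 and p48.1. Three consequences need no assumed rate: 1 scan is used of up to 9 or 10, each multi-year value equals its last one-year value, and the count can drop as the Period lengthens. The 4.6% to 34.6% range rests on independent Poisson counts with an assumed equal mean of 0.05 to 1.0 at M36 and M48. It shows scale and does not forecast this trial.

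The reach is limited to by-Period new T1 Gd+ summaries over the parent and extension period, and to CUA only if the redacted sections use these counts. Whether the Baseline–Month 24 count is itself a sum over scans cannot be checked, because the parent IAP is not among the documents. The point is worth correcting because correction is cheap, but it does not threaten the main conclusions.

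**What to change.** In SAP 9.8:
1. Restrict the last-scan rule to p12.3/p100.36 and p12.4/p100.48.
2. Define the new T1 Gd+ count for p36.1 and p48.1 as the sum of the new counts over the post-Baseline Sequential Visit Periods already defined in SAP 9.6, through p100.36 or p100.48. First check how the parent IAP derives new lesions for Periods up to Month 24, so that the two parts can be added.
3. State how not-evaluable (NE) or missing scans are handled, for example the sum of available counts with the number of contributing scans reported.
4. If CUA is reported for p36.1 or p48.1, state which counts enter it.

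If a sum is not wanted, drop the new-lesion count for p36.1 and p48.1, or label it an end-of-period count in text and tables.

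The cost is a short SAP edit and a derivation change, with no new scans. There is one small downside. SAP 9.8 makes a derived count NE when any required component is NE, so a sum would be NE more often than a last-scan count unless item 3 is adopted. The section already exempts the mean T1 Gd+ count from that rule, so a similar exemption would be in keeping.

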9.9 Data Handling in Case of PDs

Protocol Deviations (PDs) in the Extension Study will not be considered in the planned statistical analyses (i.e., all data will be analyzed independent from any reported PD). Further details on a subset of protocol deviations are described in Section 10.2.

9.10 Covariates and Stratification Factors

The following covariates are defined:

Unless otherwise specified, these factors will be obtained from the baseline information of the MAGNIFY MS Baseline.

Age

See MAGNIFY MS IAP version 3.0.

EDSS at Baseline

see MAGNIFY MS IAP version 3.0.

Pooled centers

Some centers will have few eligible participants only. Therefore, the centers will be pooled together by country except for

• sites that have more than 12 participants in the FAS (i.e., these sites will not be pooled with any other site).

Some countries will have few eligible participants only. Therefore, countries will be pooled as follows:

- Scandinavia = Finland and Sweden
- Mediterranean = Italy and Spain
- o France-UK = France and UK
- o Austria-Hungary-Czech = Austria, Hungary, and Czech Republic
- Australia-Canada = Australia and Canada

The following MRI specific covariate is defined:

Time between scans: in Years

Time between scans (in Years) is calculated as follows:

- Time between scans (in Years) = (MRI date of the Visit MRI of the previous Visit + 1) /365.25, i.e.:
 - If (Visit= Month 36) then Time between scans (in Years) = (MRI date at Month 36
 MRI date at Month 24 + 1)/365.25
 - If (Visit= Month 48) then Time between scans (in Years) = (MRI date at Month 48
 MRI date at Month 36 + 1)/ 365.25

If the corresponding MRI is available and the time between scans is missing (due to preceding MRI being missing) it will be replaced by expected time as follows:

- Month 36 Visit = 1 year
- Month 48 Visit = 1 year

For calculations for Month 1, 2, 3, 6, 12, 15, 18, 24 Visits, see MAGNIFY MS IAP version 3.0 Section 9.

9.11 Definition of Start of COVID-19 Pandemic

The start of COVID-19 pandemic will be defined by country as the earliest date of either the date of the first death from COVID-19 occurred in each country according to the published data by

European Center for Disease Prevention and Control on 26th June 2020 (https://www.ecdc.europa.eu/en/publications-data/download-todays-data-geographic-distribution-covid-19-cases-worldwide) or 11th March 2020 (when the WHO declared COVID-19 pandemic).

9.12 Visit timing with respect to COVID-19 pandemic

A visit is defined to be performed after the start of COVID-19 pandemic if the visit end date is greater than the start of COVID-19 pandemic date.

10 Study Participants

The subsections in this section include specifications for reporting participant disposition and study intervention/study discontinuations. Additionally, procedures for reporting PDs are provided.

10.1 Disposition of Participants and Discontinuations

This section describes participant disposition in the extension study.

Participant disposition in this Extension Study will be presented for the ES:

- Total number of participants enrolled in the MAGNIFY MS Extension Study (i.e., participants who gave informed consent for the Extension Study)
- Number of participants who discontinued in the Screening phase by the main reason:
 - o Subject did not meet all eligibility criteria
 - Withdrawal by subject
 - o Progressive Disease
 - o Adverse Event
 - Lost to Follow-up
 - Death
 - o Other
- Number of eligible participants in the Extension Study, overall and by the following categories:
 - Number and percentage of eligible participants enrolled before the start of COVID-19
 - Number and percentage of eligible participants ongoing at data cut-off (applicable to IAs only)
 - o Number and percentage of eligible participants who completed the study
 - Number and percentage of eligible participants who discontinued the study, with the primary reason of discontinuation:
 - Withdrawal by subject

- Progressive disease
- Adverse event
- Lost to follow-up
- Death
- Protocol non-compliance
- Other

The duration of gap period between MAGNIFY MS Trial and MAGNIFY Extension Study Baseline will be summarized using the following classes:

- o No gap (i.e., Month 24 Visit and Extension Baseline coincide)
- o Duration of gap period < 1 month
- o Duration of gap period ≥ 1 month and ≤ 3 months
- o Duration of gap period ≥ 3 months and < 6 months
- O Duration of gap period ≥ 6 months and ≤ 9 months
- o Duration of gap period ≥ 9 months and ≤ 12 months
- o Duration of gap period > 12 months

Additionally, duration of gap period will be summarized using descriptive statistics.

Percentages will be presented with respect to the number of eligible participants.

The number of participants in each analysis set will be provided overall, by region, by country within region and by site.

The following participant data listings will be provided:

- Listing of discontinued participants for the FAS,
- Listing of participants excluded from the Analysis Sets.

10.2 Protocol Deviations / Exclusion from Analysis Sets

10.2.1 Important Protocol Deviations

Important protocol deviations (IPDs) are a subset of protocol deviations that might significantly affect the completeness, accuracy, and/or reliability of the study data or that might significantly affect a participant's rights, safety, or well-being.

Important protocol deviations will be identified for all participants by either site monitoring, medical review processes or programming and confirmed prior to or at the Data Review Meeting at the latest.

Any IPD is documented in SDTM datasets whether identified through site monitoring, medical review or programming. The management of protocol deviations is outside of this IAP document.

The following summary tables and listings of IPDs will be provided for the FAS:

- Number and proportion of participants with IPDs by classification of IPDs (overall and based on relationship to COVID-19 pandemic),
- Listing of IPDs (including information regarding relationship to COVID-19 pandemic).

10.2.2 Reasons Leading to the Exclusion from an Analysis Set

A frequency table, as well as a listing, organized according to reasons for exclusion from the FAS and TCS, respectively, will be provided, if applicable.

Possible reasons for exclusion from the FAS include:

- Not fulfill any of the inclusion criteria
 - o Participants of the MAGNIFY MS trial who received at least a single dose of cladribine tablets during the MAGNIFY MS trial
 - O Data on MRI is available/acquired from at least parent study Month 18 or Month 24 visit
 - o Data on EDSS and relapse is available/acquired from parent study Month 24 visit
 - o Capable of giving signed informed consent
- Meet any of the exclusion criteria
 - o Participant is considered by the Investigator, for any reason, to be an unsuitable candidate for the study
 - Participation in other studies/trials

Possible reasons for exclusion from the TCS include:

- Participants are not included in the FAS
- Participants did not complete the full treatment course of the first and second year in the parent study

11 Demographics and Other Baseline Characteristics

If not stated otherwise, the following analyses will be performed based on the FAS.

11.1 Demographics

Demographic characteristics will be summarized descriptively using the information from the Screening/Baseline Visit eCRF pages in the MAGNIFY MS trial. The data will be presented in a summary table as well as a listing as specified in MAGNIFY MS IAP version 3.0. In addition, age at time of informed consent as collected from the "Demographics" eCRF page in the MAGNIFY MS Extension Study will be added in both the summary table and the listing.

11.2 Medical History

The medical history will be summarized from the "Medical History" eCRF page of the MAGNIFY MS Extension Baseline, using the most recent Medical Dictionary for Regulatory Activities (MedDRA) version at time of database lock, preferred term (PT) as event category and system organ class (SOC) body term as Body System category. Each participant will be counted only once within each PT or SOC.

Additionally, also the medical history from the "Medical History" eCRF page of the MAGNIFY MS Baseline, using the MedDRA version that has been applied for coding of Medical History in the parent study, will be summarized as well.

Medical history will be displayed in terms of frequency tables: ordered by primary SOC and PT in alphabetical order.

11.3 Other Baseline Characteristics

Other baseline characteristics at MAGNIFY MS Baseline, including MS Disease Characteristics, MRI Baseline Characteristics and Vital Signs, will be presented as specified in MAGNIFY MS IAP version 3.0.

EDSS assessment at Extension Baseline Visit was performed for almost all participants, regardless of whether they had a gap period, and will be listed only. The EDSS scores of participants who had a gap period will still be considered for determining disease progression, as planned in the CSP.

12 Previous or Concomitant Therapies/Procedures

Relevant previous medications at MAGNIFY MS Baseline will be summarized as specified in MAGNIFY MS IAP version 3.0.

Concomitant medications are medications, other than study medications, which are taken by participants after the initial dose of cladribine tablets (including the study period of the MAGNIFY MS trial and the Extension Study which is including the gap period between the MAGNIFY MS trial and MAGNIFY MS Extension Study).

Concomitant medications will be summarized separately for the study period of the MAGNIFY MS trial and the Extension Study Period.

Data will be used from the "Concomitant medication" eCRF page of the MAGNIFY MS trial and the Extension Study. All medications entered into the "Concomitant medication" eCRF page will be assumed to be "concomitant" irrespective of the actual start and end dates.

Anatomical Therapeutic Chemical classification (ATC)-1st level and PT will be tabulated as given from the World Health Organization Drug Dictionary (WHO-DD) dictionary. In case multiple ATCs are assigned to a drug, all ATC-1st level will be used for reporting.

The most current WHO-DD dictionary version at time of MAGNIFY Extension Study analysis data base lock will be used only for MAGNIFY MS Extension Study. For MAGNIFY MS parent study, the version of that has been used for coding of concomitant medications will apply. The WHO-DD dictionary used for coding will be listed as a footnote of corresponding table or listing.

Additionally, all DMDs which have been reported for the study period of the MAGNIFY MS trial and the MAGNIFY MS Extension Study will be presented together by PT. The updated list of DMDs (see Appendix 18.1) will be used to identify DMD in concomitant medications in MAGNIFY MS Extension Study instead of the parent study DMD list (see MAGNIFY MS IAP version 3.0). List could further be updated before database lock.

Concomitant procedures which were undertaken any time during the Extension Study Period will be listed by participant for the SAF.

13 Study Intervention: Compliance and Exposure

As no treatment is provided in the Extension Study, participants' compliance and exposure in the MAGNIFY MS trial will be presented for the Extension Study SAF as defined in MAGNIFY MS IAP version 3.0.

14 Efficacy Analyses

The following analyses will be performed based on the FAS except when otherwise stated.

For the detailed definition of covariates and stratification factors that are used in the statistical models see Section 9.10. Details about the derived MRI endpoints and general handling of MRI data is described in Section 9.8.

Descriptive summary statistics will be presented for the absolute values and the changes from Baseline as applicable by Visit [Protocol Scheduled Visits except for Baseline (defined in Section 9.1)] for all efficacy endpoints (and the components, where applicable) for the FAS and respective subgroups for which the variables are analyzed. Details about the presentation of continuous and categorical variables are given in Section 9.

Wherever possible, all estimated results from the statistical models will be calculated with the same observed margin which reflects the population of the whole corresponding analysis set, regardless of missing data (as described in MAGNIFY MS IAP version 3.0).

14.1 Primary Endpoint: Proportion of participants with No Evidence of Disease Activity (three parameter [NEDA-3]) during Year 3 Visit and Year 4 Visit Period after the initial dose of cladribine tablets

The primary endpoint for the Extension Study is defined as the proportion of participants with NEDA-3 during Year 3 Visit and Year 4 Visit Period after the initial dose of cladribine tablets, i.e., NEDA-3 during the following period will be evaluated:

• Year 3 Visit and Year 4 Visit Period (i.e., Extension Study Period)

For the detailed definition of Periods, see Section 9.6.

